2.5.3 Interim analyses and data monitoring

No interim analysis is planned.

2.5.4 Multiple comparisons/ multiplicity issues

There are no multiplicity issues in this study.

Sponsor: MMI Product: Symani system for microsurgical anastomosis Study: PRIMO	
Statistical Analysis Plan Final 22 November 2024	

2.5.5 Windows for time points

All data are expected to be collected within a timeframe of 30 \pm 7 days from the initial study procedure (or 24 weeks \pm 2 weeks for lymphatic surgery). If a patient has a revision procedure where the revision is to a robotic anastomosis, then the timeframe for data collection will be 30-days from the date of the last revision procedure (revision to a robotic anastomosis), where the date of re-operation is prior to the date of discharge. However, for the retrospective data collection, available data will be used whenever possible. Data may not be available at 30 days post-operation.

2.5.6 Statistical technical issues

The models noted in the efficacy analyses propose a default covariance structure of type=VC, which is a simple diagonal matrix with equal variances across all levels of the surgeon ID variable. This will be examined to determine if the structure is appropriate, or whether an alternative structure is more appropriate. The use of the GROUP= option in the random statement may also be investigated if type=VC does not adequately explain the variance observed across surgeons (that is, including GROUP=surgeon in the random statement). This will be done as part of normal model checking procedures and described as part of the reported statistical analysis results.

The retrospective data collection may have a reasonable amount of missing data. All data available will be used as much as possible and the derivation of the effectiveness endpoints defines how to obtain a result if possible. All data summaries will clearly indicate the amount of missing data.

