2.4.4 Analysis of effectiveness variables

Note on analysis models/approach.

For all binary outcomes a simple frequency table presenting number and percentage (with confidence limits) will be produced, where the denominator will be the unit of analysis (patient, surgery type, procedure or anastomosis). The confidence limits produced will be biased as they assume independent observations whilst repeat assessments on the same patient (ie > 1 anastomosis/procedure, >1 procedure/patient) are not independent.

To explore the extent of dependence in the data, a table will be produced to describe the hierarchy in the data (as per fig 1), namely:

- Number of patients.
- Number of surgery types (flap, replantation, lymphatic)/patient (i.e. 1, 2 or 3 different types of surgery).
- Within surgery type, number of procedures/patient (i.e. number of flaps, number of replantations, number of lymphatic procedures).
- Within each procedure, number of anastomoses/procedure and also number of anastomoses/patient.

In the simplest scenario there will be one surgery type/patient, one procedure/patient and for that procedure only one anastomosis (so at all levels there is one/patient).

The most complex structure is each patient has all three surgery types, with multiple procedures of each type and for each procedure there are multiple anastomoses.

In addition to these levels of dependence due to repeated observations on the same patient, the results are expected to be influenced by surgeon. Accordingly, for the main analysis of all effectiveness endpoints, a mixed model will be employed where surgeon will be included as a random term.

All models will be fitted separately for each surgery type (free flaps, replantations, lymphatic).

In all models fixed effects for subpopulation (prospective/retrospective) and recipient site/location will also be included to facilitate estimation by subpopulation and recipient site/location. For analysis of replantations a further fixed effect will be included for procedure type (free or nerve).

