2.4.4.1 Analysis of primary effectiveness variable – procedure robotic success

As per section 2.1.3.1 each anastomosis for each patient in the FAS will be assigned to ‘Yes’ or ‘No’ for procedure robotic success. This represents a binary outcome. The analysis of this variable is at the anastomosis level.

For each surgery type (replantation, free flap or lymphatic surgery) stratified frequency tables will be presented stratified by subpopulation (prospective/retrospective) and recipient site/location. The denominator is the number of anastomoses. The proportion of anastomoses classified as a robotic success by stratum and overall for each surgery type will be presented with 95% confidence limits. Results will also be presented on a forest plot.

For replantations a further stratifying variable will be included, namely procedure type (free/nerve).

For each surgery type, a generalized linear mixed model (GLMM) will be used to estimate the percentage of anastomoses classified as robotic success. In SAS, PROC GLIMMIX will be utilized to analyze the data. Subpopulation (prospective/retrospective), recipient site/location and surgeon experience will be included as fixed effects, and surgeon as a random effect. Procedure number (within a surgery type) and anastomosis number (within a procedure) will be included as random terms to acknowledge the dependence in the data (see note above). From the model the adjusted rate of robotic success will be obtained, with 95% confidence limits, for each type of surgery overall and by recipient site/location, by surgeon experience and by subpopulation. (Model 1).

Fixed effects

For free flaps, recipient site will be head and neck, extremities, breast or other.

For lymphatic surgery location will be heads and neck, upper limbs or lower limbs

For replantations there will also be a factor for procedure type (free or nerve), as well as recipient site (as for free flaps) (Model 1a) and results also obtained by procedure type (free/nerve).

For all types of surgery, surgeon experience is classified as microsurgeon, fellow, resident.

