2.5 Statistical/ Analytical Issues

2.5.1 Adjustments for covariates

Surgery type (flap, replantation, lymphatic) and subpopulation (prospective/retrospective) are included as fixed factors where applicable in the primary and secondary efficacy modelling. Results by these factors are included in tables and forest plots produced for the study.

Surgeon is included as a random effects term in each of the models.

Procedure number/anastomosis number (within patient) are included in models where relevant to acknowledge dependence in the data.

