Appendix 1. Summary of endpoints, unit of analysis and analysis method

Endpoint	Level	analysis
Robotic success	Anastomosis	GLMM. Bernoulli form by stype Fixed: recipient site/location, subpop For replantations also include procedure type (free or nerve) Random surgeon, procedure number anastomosis number, subject=patient. Model 1/1a.
Robotic usability	Patient	GLMM Binomial form as nsuccess/npats by stype Fixed: recipient site/location. For replantations also include procedure type (free or nerve) Random surgeon. Model 2./2a
Anastomosis time	Anastomosis	GLMM normal by stype Fixed: recipient site/location, subpop For replantations also include procedure type (free or nerve) Random surgeon, procedure number anastomosis number, subject=patient. Model 3/3a
Intra-operative redo	Anastomosis	Model 1/1a
Post-op redo	Procedure	GLMM Bernoulli form by stype Fixed: recipient site/location, subpop For replantations also include procedure type (free or nerve),

Sponsor: MMI Product: Symani system for microsurgical anastomosis Study: PRIMO	
Statistical Analysis Plan Final 22 November 2024	

		Random surgeon, procedure number subject=patient. Model 4/4a
Complications	Patient	Safety endpoint. Summaries of AEs
Warm ischemia time		
Flap loss/failure	Procedure	Model 4/4a
Limb volume reduction	Procedure	GLMM normal Fixed timepoint. Cov baseline vol. Random surgeon, procedure number subject=patient. Model 5.
Free flap viability at 30 days	Procedure	Model 4/4a
Intra-operative anastomosis patency	Anastomosis	Model 1/1a
Rate of intra-operative approach change	Anastomosis	Model 1/1a
Freedom from device related SAE at discharge	Patient	Simple frequency and exact CL
Freedom from device related AE at discharge	Patient	Simple frequency and exact CL
All cause re-admission rate	Patient	KM. Use PL to get rate within 30 days
All cause re-op rate	Patient	KM. Use PL to get rate within 30 days
All cause mortality rate	Patient	KM. Use PL to get rate within 30 days
Length of hospital stay	Patient	Descriptive stats

PRIMO Statistical Analysis Plan

Final Audit Report

2024-12-13

Created:	2024-12-11
By:	[name] ([contact])
Status:	Signed
Transaction ID:	CBJCHBCAABAAHjF3YtYJkG7xb1_tZngZ89-skKZM8HiF

"PRIMO Statistical Analysis Plan" History

-  Document created by [name] ([contact])
2024-12-11 - 4:57:01 PM GMT
-  Document emailed to [name] ([contact]) for signature
2024-12-11 - 4:57:09 PM GMT
-  Document emailed to [name] ([contact]) for signature

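### The fallback in SAP Section 2.5.6 of a separate variance for each surgeon would, if adopted, give model-adjusted estimates with confidence limits that under-cover

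*SAP*

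**What the plan says.** Section 2.4.4 expects surgeons to affect the results. It warns that simple limits which treat observations as independent are biased. For the main analysis of all effectiveness endpoints it therefore states that "a mixed model will be employed where surgeon will be included as a random term". Section 2.5.1 repeats this: "Surgeon is included as a random effects term in each of the models".

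Section 2.5.6 sets the default covariance structure to type=VC, described as "a simple diagonal matrix with equal variances across all levels of the surgeon ID variable". It then adds: "The use of the GROUP= option in the random statement may also be investigated if type=VC does not adequately explain the variance observed across surgeons", and spells the option out as "including GROUP=surgeon in the random statement". This is presented as part of routine model checking, to be described with the results. No criterion for adopting the option is given.

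The models feed reported results. For the primary endpoint (Section 2.4.4.1): "From the model the adjusted rate of robotic success will be obtained, with 95% confidence limits". Appendix 1 gives the random part of that model as "Random surgeon, procedure number anastomosis number, subject=patient. Model 1/1a". For robotic usability (Model 2, Section 2.4.4.2.1 and Appendix 1), the data are aggregated to counts per surgeon and surgeon is the only random term.

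**The concern.** The random surgeon effect is the SAP's remedy for clustering by surgeon. It works because one variance, estimated from all surgeons together, enters the standard error of the adjusted rate or mean. A random intercept has only one realised value per surgeon, so a separate variance for each surgeon has one observation behind it. The common variance disappears, and with it much of the allowance for surgeons who differ.

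At stake are the model-adjusted estimates and limits in Sections 2.4.4.1 to 2.4.4.2.8. A surgeon with unusually poor results would lose weight while the interval narrowed, which is false precision about performance across surgeons. Models are fitted separately by surgery type, so each has fewer surgeons than the study as a whole.

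**Working it through.** **Plan's own figure.** Section 2.5.6 gives none, so there is nothing to reproduce.

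**Inputs.** From the SAP: 402 patients as the minimum (Section 1.7), a reference rate of 85% (Section 1.7), and the default and fallback structures (Section 2.5.6). Assumed, because the documents are silent: 6 to 20 surgeons, a surgeon ICC of 0.02 to 0.20 on a continuous scale, or a surgeon SD of 0.3 to 1.0 on the logit scale.

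**Step 1, mechanism.** Let surgeon s have mean y_s, deviation d_s = y_s − μ from the fitted centre, and within-surgeon sampling variance v.
- Common variance: Var(y_s) = τ² + v, with τ² estimated from all surgeons.
- GROUP=surgeon: the maximum-likelihood (ML) estimate is τ_s² = max(0, d_s² − v). The weight is therefore 1/max(v, d_s²), and the standard error is 1/√(sum of weights).

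**Step 2, one worked setting.** Take 10 surgeons, 402/10 = 40.2 observations each, ICC 0.10 and total variance 1.
- v = 0.90/40.2 = 0.0224.
- Common variance: every surgeon has weight 1/(0.10 + 0.0224) = 8.2.
- GROUP=surgeon: a surgeon near the centre has weight 1/0.0224 = 44.7. A surgeon two between-surgeon SDs away has d² = 4 × 0.10 = 0.40 and weight 1/0.40 = 2.5, about 18 times less.
- Ignoring surgeon altogether, SE = √(0.0224/10) = 0.047.
- Simulated by ML, 2,000 runs: mean SE is 0.103 with a common variance and 0.063 with GROUP=surgeon. The fallback thus moves the SE (0.103 − 0.063)/(0.103 − 0.047) = 71% of the way to ignoring surgeon.
- The GROUP=surgeon estimate is also noisier. Its actual SD is 0.165, against 0.109 with a common variance, so its reported SE is 0.063/0.165 = 0.38 of what it should be. Coverage with z limits falls from 90% to 53%. Restricted ML (REML) gives 92% to 53%.

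**Step 3, coverage over a grid.** Normal approximation, balanced surgeons, t(S−1) limits for S surgeons, 2,000 runs per cell, GROUP=surgeon applied in every run:

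| Surgeons × observations | ICC 0.05 | ICC 0.10 | ICC 0.20 |
|---|---|---|---|
| 8 × 50 | 74% | 58% | 45% |
| 12 × 35 | 76% | 61% | 48% |
| 20 × 20 | 81% | 69% | 54% |

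Repeat runs agree within about 3 percentage points. At ICC 0.02 coverage is 86-89%. One common variance with the same t limits gives about 95% throughout. Over the tabulated cells, the half-width under GROUP=surgeon is 17-59% smaller.

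**Step 4, binary outcome.** Logistic random-intercept model, 402 anastomoses, true conditional rate 85%, z limits, 250 runs per cell. Coverage, common variance → GROUP=surgeon:

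| Surgeons | Logit SD 0.3 | Logit SD 0.6 | Logit SD 1.0 |
|---|---|---|---|
| 6 | 90% → 80% | 89% → 61% | 89% → 42% |
| 10 | 92% → 87% | 90% → 60% | 86% → 56% |
| 20 | 92% → 86% | 92% → 76% | 91% → 62% |

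Between 47% and 69% of the surgeon variances were estimated as zero. With t limits the common-variance model covers 94-96% and GROUP=surgeon 55-91%.

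**Limits of the check.** SAS was not run, and fixed effects and patient-level random terms were left out.

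**The case against.** **It is optional and disclosed.** The default is already a common variance, and the fallback is conditional and would be reported. This stands: the defect is in a permitted option, not in the planned main model. Disclosure would not repair the limits, however, and the SAP gives no rule for adopting the option.

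**The simulations apply the option where its trigger should not be met.** They draw all surgeons from one distribution, so the common variance is correct. How often the fallback would be adopted depends on the selection rule. Over the layouts in step 3 at ICC 0.05-0.20, AIC preferred GROUP=surgeon in 0-3% of runs when every surgeon variance was counted as a parameter. When only non-zero variances were counted, it did so in 13-56%. This stands too: the coverage figures are conditional on adoption. But if surgeons truly had unequal variances, one realised effect each would still not estimate them.

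**The coding of Model 1 is ambiguous.** Appendix 1 puts surgeon in one line with subject=patient. Read literally, that nests the surgeon effect in patient, and GROUP=surgeon would then rest on many patients per surgeon. The mechanism above would not apply, although surgeon clustering would then be handled wrongly for another reason. Section 2.5.6 speaks of levels of the surgeon variable, which favours the reading used here. In Model 2 surgeon is the only random term, so no harmless reading is available.

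**A reader might infer that the superiority claim against 85% is at risk.** The documents do not support that. Section 1.7 bases the claim on exact limits, which do not use the mixed model.

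**A reader might also infer that intervals always become far too narrow.** They do not. At a logit SD of 0.3 the two standard errors are about equal (median ratio 1.00-1.04), and coverage falls only to 80-87%.

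**Conclusion.** The point holds in limited form, and the label is wrong as written, for a permitted fallback and not for the default model. GROUP=surgeon on the surgeon intercept is unavoidable in Model 2 if the option is used, and it is the natural reading of Section 2.5.6 for the other models. It largely removes between-surgeon spread from the standard error, though not all of it.

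If the option were adopted, nominal 95% limits would cover about 86-89% at ICC 0.02 and about 45-80% at ICC 0.05-0.20, against about 95% for a common variance with t limits. These figures assume 8 to 20 balanced surgeons, a normal approximation and the option always applied. The 95% benchmark also needs t limits, which the SAP does not specify. With z limits the common-variance logistic model covered 86-92%.

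The harm is confined to the model-adjusted rates and means. Neither the exact-limit rule in Section 1.7 nor the simple tabulated proportions use this random statement.

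**What to change.** In Section 2.5.6, delete GROUP=surgeon for the surgeon random effect. State that all reported adjusted estimates and limits come from the model with one common between-surgeon variance. In Appendix 1, put the surgeon intercept in its own RANDOM statement, apart from the patient-level terms that carry subject=patient.

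If heterogeneity between surgeons needs exploring, do so only as a sensitivity analysis that leaves out one surgeon at a time, or by GROUP= on patient-level terms, where each variance rests on many patients.

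The cost is a few sentences in the SAP and no new data. Intervals will be wider than under the fallback.

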3. SOFTWARE DOCUMENTATION

All summaries and statistical analyses will be generated using SAS version 9.4 or higher. All figures will be generated using SAS 9.4 or higher.

Appendix 1. Summary of endpoints, unit of analysis and analysis method

Endpoint	Level	analysis
Robotic success	Anastomosis	GLMM. Bernoulli form by stype Fixed: recipient site/location, subpop For replantations also include procedure type (free or nerve) Random surgeon, procedure number anastomosis number, subject=patient. Model 1/1a.
Robotic usability	Patient	GLMM Binomial form as nsuccess/npats by stype Fixed: recipient site/location. For replantations also include procedure type (free or nerve) Random surgeon. Model 2./2a
Anastomosis time	Anastomosis	GLMM normal by stype Fixed: recipient site/location, subpop For replantations also include procedure type (free or nerve) Random surgeon, procedure number anastomosis number, subject=patient. Model 3/3a
Intra-operative redo	Anastomosis	Model 1/1a
Post-op redo	Procedure	GLMM Bernoulli form by stype Fixed: recipient site/location, subpop For replantations also include procedure type (free or nerve),

Sponsor: MMI Product: Symani system for microsurgical anastomosis Study: PRIMO	
Statistical Analysis Plan Final 22 November 2024	

		Random surgeon, procedure number subject=patient. Model 4/4a
Complications	Patient	Safety endpoint. Summaries of AEs
Warm ischemia time		
Flap loss/failure	Procedure	Model 4/4a
Limb volume reduction	Procedure	GLMM normal Fixed timepoint. Cov baseline vol. Random surgeon, procedure number subject=patient. Model 5.
Free flap viability at 30 days	Procedure	Model 4/4a
Intra-operative anastomosis patency	Anastomosis	Model 1/1a
Rate of intra-operative approach change	Anastomosis	Model 1/1a
Freedom from device related SAE at discharge	Patient	Simple frequency and exact CL
Freedom from device related AE at discharge	Patient	Simple frequency and exact CL
All cause re-admission rate	Patient	KM. Use PL to get rate within 30 days
All cause re-op rate	Patient	KM. Use PL to get rate within 30 days
All cause mortality rate	Patient	KM. Use PL to get rate within 30 days
Length of hospital stay	Patient	Descriptive stats

PRIMO Statistical Analysis Plan

Final Audit Report

2024-12-13

Created:	2024-12-11
By:	[name] ([contact])
Status:	Signed
Transaction ID:	CBJCHBCAABAAHjF3YtYJkG7xb1_tZngZ89-skKZM8HiF

"PRIMO Statistical Analysis Plan" History

-  Document created by [name] ([contact])
2024-12-11 - 4:57:01 PM GMT
-  Document emailed to [name] ([contact]) for signature
2024-12-11 - 4:57:09 PM GMT
-  Document emailed to [name] ([contact]) for signature
